**Purpose:**

To evaluate the efficacy and safety of the Clear & Brilliant® Permea laser in combination with topical cysteamine for the treatment of melasma of the face.

**Objectives:**

- A. To evaluate the efficacy of the Clear & Brilliant Permea laser system in combination with topical cysteamine
  - a. To assess for improvement of melasma after completion of three treatments as determined by the treating clinician and objective measures
  - b. To evaluate subject's satisfaction with melasma treatment and assessment of improvement after three treatments
  - c. To evaluate the length of treatment.
- B. To evaluate the safety of melasma treatment in all skin types using the Clear & Brilliant Permea laser in combination with topical cysteamine
  - a. To evaluate the immediate response to treatment
  - b. To evaluate the subject's assessment of comfort associated with treatments
  - c. To determine the rate of adverse events for the treatment group as a whole

**Study Design:** Single Center, Prospective, With Before-After Analysis

**Study population:** Twenty healthy male or female patients, 18-74 years of age, of all skin types with melasma on the face that wish to be treated. Each subject will receive topical cysteamine cream which they will be instructed to use once a day at home. In addition, one side of the face will be randomly selected for treatment with laser. Patients will receive three monthly treatments, at 4-6 week intervals, on the selected side of the face with the Clear & Brilliant Permea laser. The treatment duration including pre and post treatment procedures is estimated to be 90 minutes per subject. Subjects will return for a follow-up visit 3 months after the initial treatment for a total of four visits. The treatment plan will be the same regardless of the subject's skin type. Four passes, at high setting will be performed.

During the first and fourth visit, the areas of treatment will be photographed with a digital camera under controlled conditions. Subject improvement will be assessed via investigator and subject grading at visit 1 and 4. Improvement in melasma will be assessed by blinded evaluators who will review pre and post treatment photographs taken with VISIA® Skin Analysis System for facial imaging (Canfield Scientific Inc) from visit 1 and 4. Side effects (including pain, redness, dryness, and hyperpigmentation) will be assessed and recorded at visits 2, 3, 4.

Research Coordinators and Investigators who are all listed in the IRB-approved research protocol will obtain informed consent. Both a research assistant and an M.D. Investigator will be available to discuss the consent. Criteria for study inclusion will include subjects with melasma on the face. They will be followed through to completion at the one month follow up.

The study device is not subject to IDE regulations because devices used are not diagnostic devices and are not undergoing consumer preference testing. The study is exempt from IDE regulations.

They will be recruited by offering participation to existing subjects at Union Square Laser Dermatology, by referrals, and by online advertisements.

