#### **Background:**

Melasma is a commonly acquired hyperpigmentary condition characterized by brown spots on sun exposed areas of the face. Treatment of melasma can be challenging as many patients are refractory to therapy, while others experience a chronic or relapsing course. Melasma also significantly impact patients' quality of life with many reporting feelings of frustration, embarrassment, and depression related to their condition. Mainstay of treatment includes topical skin-lightening and brightening agents such as hydroquinone, tranexamic acid, retinoids, azelaic, kojic and ascorbic acids, as well as various chemical peels, laser and light-based therapies. Current gold standard is a triple combination cream consisting of topical hydroquinone, tretinoin, and fluocinolone, along with broad-spectrum sunscreen. However, use of topical hydroquinone is associated with adverse events including irritation and a paradoxical exogenous ochronosis with prolonged use, making its use challenging. Hence, for this difficult, and often recalcitrant disease, additional therapeutic options are needed.

Topical cysteamine is safe, generally well tolerated, and can be used continuously without treatment holidays. Multiple studies have demonstrated its efficacy in the treatment of melasma, including two double-blind, randomized, and placebo controlled clinical trials. Combination therapy of lasers with lightening agents have been shown to augment melasma treatment. However, data on combination laser and topical cysteamine is sparse, and no controlled or split-faced studies have been published. Thus, we aim to investigate combined topical cysteamine with laser, compared with topical cysteamine alone to assess whether this adjuvant therapy can improve the efficacy of cysteamine in the treatment of melasma.

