**Table. Determination of the Modified MASI (mMASI) Score**

Location of Melasma	Scoring a	Calculation for Total Score b
Forehead	(0.3) (A) (D)	
Left malar	(0.3) (A) (D)	Forehead mMASI Score + Left Malar mMASI Score + Right Malar mMASI Score + Chin mMASI Score = Total mMASI Score
Right malar	(0.3) (A) (D)	
Chin	(0.1) (A) (D)	

Abbreviation: MASI, Melasma Area and Severity Index.

a Scoring system: A, Area of involvement rated 0 to 6: 0 indicates absent; 1, <10%; 2, 10% to 29%; 3, 30% to 49%; 4, 50% to 69%; 5, 70% to 89%; 6, 90% to 100%. D, Darkness rated 0 to 4: 0 indicates absent; 1, slight; 2, mild; 3, marked; 4, severe.

b Total mMASI score range is 0 to 24 and calculated by adding scores for 4 areas of the face.

Safety Endpoints:

- Incidence of adverse safety events during the treatment and follow up period
- Subject assessment of pain and discomfort associated with treatments using an 11-point visual assessment scale (VAS) pain score

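### The safety objective asks for one adverse-event rate for the whole group, and no safety endpoint uses the randomised cysteamine-only side, so the safety results cannot show what the laser adds

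*Protocol*

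**What the plan says.** Under Objectives in the protocol, the parent safety objective B is "To evaluate the safety of melasma treatment in all skin types using the Clear & Brilliant Permea laser in combination with topical cysteamine". Its third part, B.c, is "To determine the rate of adverse events for the treatment group as a whole".

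The Study population paragraph sets a split-face design. All patients get the cream ("Each subject will receive topical cysteamine cream which they will be instructed to use once a day at home"), and "one side of the face will be randomly selected for treatment with laser". The Background gives the question: "we aim to investigate combined topical cysteamine with laser, compared with topical cysteamine alone". The hypotheses that follow apply that contrast to mMASI and to patient satisfaction, not to safety.

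The Safety Endpoints are "Incidence of adverse safety events during the treatment and follow up period" and "Subject assessment of pain and discomfort associated with treatments using an 11-point visual assessment scale (VAS) pain score". The Study population paragraph adds "Side effects (including pain, redness, dryness, and hyperpigmentation) will be assessed and recorded at visits 2, 3, 4". The Safety Analysis section has reactions graded from 0 to 4 on the case report form at each treatment and follow-up visit. None of these names a side of the face or a comparison between sides.

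**The concern.** The trial has no separate treated and control groups of patients: both regimens sit on the same face. One rate per patient counts someone with a reaction on the lasered side only, on the cysteamine-only side only, or on both, in the same way.

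The cream has local reactions of its own. Risks and Discomforts lists short-lived irritation and burning for the topical, and pain, redness, swelling and blistering for the laser. Burning, discomfort and redness on a face treated with both are hard to attribute from the type of event alone. The side on which they occur is the information that randomisation makes usable.

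At stake is whether the trial, which asks for efficacy what the laser adds to cysteamine, can say the same about local tolerability. The design already supplies the control, but the safety section does not call on it.

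**Working it through.** **Plan's own figure.** The protocol states no adverse-event rate and no between-side safety difference, so there is nothing to reproduce. The only figure used is the planned 20 patients (Sample Size Calculation). All event counts below are assumptions.

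**Notation.** Among n = 20 patients, let b have a local event on the lasered side only, c on the cysteamine-only side only, and e on both sides.

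- Per-patient rate = (b + c + e)/n
- Lasered-side rate = (b + e)/n
- Cysteamine-only-side rate = (c + e)/n
- Paired difference = (b − c)/n

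The per-patient rate fixes only the sum b + c + e. It does not fix b − c.

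**Assumed total.** Let 12 patients have any local event, so the per-patient rate is 12/20 = 60%. The exact (Clopper-Pearson) 95% limits are the 2.5% point of Beta(12, 9), 0.361, and the 97.5% point of Beta(13, 8), 0.809. The interval is 36% to 81%.

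**Four ways to reach the same 60%**

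| b | c | e | Per patient | Lasered side | Cysteamine-only side | Difference (points) | Exact McNemar p |
|---|---|---|---|---|---|---|---|
| 10 | 0 | 2 | 60% | 60% | 10% | +50 | 0.002 |
| 6 | 0 | 6 | 60% | 60% | 30% | +30 | 0.031 |
| 2 | 2 | 8 | 60% | 50% | 50% | 0 | 1 |
| 0 | 0 | 12 | 60% | 60% | 60% | 0 | 1 |

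The p-values are two-sided binomial on the discordant pairs: 2 × 0.5^10 = 0.00195 in the first row and 2 × 0.5^6 = 0.03125 in the second. The reported rate and its interval are the same in all four rows, while the added risk runs from 0 to 50 points.

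**What is lost.** Whenever c = 0, the per-patient rate equals the lasered-side rate. The gap is then the missing comparator, not a distorted figure for the lasered side.

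**What a by-side analysis could deliver at n = 20.** Power of the exact McNemar test at two-sided 5% is the sum, over all (b, c) with p ≤ 0.05, of the multinomial probability of (b, c, 20 − b − c).

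| Probability lasered side only | Probability cysteamine-only side only | Power |
|---|---|---|
| 0.20 | 0.05 | about 10% |
| 0.30 | 0.05 | about 32% |
| 0.40 | 0.05 | about 58% |
| 0.50 | 0.05 | about 79% |

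A test would miss most moderate differences. The by-side result is worth having as an estimate with an interval.

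**The case against.** A reader might infer that the protocol deliberately prescribes merging the two sides. The text does not support that. B.c sits under an objective about all skin types, so its closing words can naturally mean across skin types, or the combination regimen as such. Objective B, like both Purpose statements, frames safety as that of the combination, and a rate per patient answers that. This stands: the objective is not an error in its own terms.

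A reader might also infer that the contrast could never be recovered. That goes too far. The Photographs section has left, right and front views taken at each visit, partly to look at side effects, so visible reactions are partly documented by side. The case report form is not shown and may already hold a side field. The limits of the photographs also stand: they do not show burning or pain, and they are timed before treatment, so a reaction that settles between visits would not appear.

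Nor does every pattern of events involve mixing of sources. If 6 of 20 patients react on the lasered side only, the per-patient 30% is also the lasered-side rate. Some events can be attributed by type, and Complications requires a judgement on whether serious events are due to the laser.

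Finally, by-side tabulation could be left to a statistical analysis plan. For the table itself that is fair. But such a plan can split only what was collected, and the recording instructions and the objective belong to the protocol.

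**Conclusion.** The point holds as an inexpensive improvement, not as a flaw that invalidates the safety results. As written, the safety objective and endpoints can describe how often patients on this regimen have events. They cannot show how much of that the laser adds to cysteamine. Under the assumed 12 of 20, an identical reported 60% fits an added local risk of 0 or of 50 points.

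This rests on assumed counts, on 20 patients all contributing both sides, and on local events only; systemic events have no side. It does not depend on which reading of B.c is right, because under any of them no safety objective, endpoint or grading instruction names the control side. Efficacy is unaffected.

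**What to change.** - Keep the per-patient rate for all events, and state in B.c what the whole group refers to.
- Add to B.c and the Safety Endpoints: local event rates on the lasered and on the cysteamine-only side, with the paired difference and an exact 95% interval, described as an estimate and not a powered test.
- Record the side for each local event, each 0-4 grade and, where it can be localised, pain. Report non-local events per patient only.
- Include in the by-side table the reactions that the Safety Analysis section counts as response to treatment and not as adverse device effects. Otherwise discomfort, prolonged redness, itching, blistering and dryness could drop out of the comparison.
- Use the left and right photographs to support visible reactions, not as a substitute for recording side.

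The cost is one side field on the case report form, if it is not already there, and one table. No extra visits or patients are needed. The downside is wide intervals at 20 patients, which the report should acknowledge.

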#### Visit 2 and 3 (Week 4 and 8)

- Assess side-effects of the treatment at initial visit
- See how tall subject is and how much subject weighs
- Perform treatment according to guidelines stated in protocol
- Schedule the next study visit
- Take photos of face

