#### Visit 4 (Week 12)

- Assess side-effects of treatment
- See how tall subject is and how much subject weighs
- Take photos of face
- Perform grading of melasma
- Post-treatment questionnaire
- Evaluation of photos comparing visit 1 and 4 to be performed

**Risks and Discomforts:** Blistering, edema, erythema and local pain are typical reactions to laser treatment. A lesser possibility exists for hyperpigmentation, hypopigmentation scarring, and/or infection. These conditions may or may not resolve over time. As with any method of tissue destruction, there is a risk of infection and of scarring, which is minimized with proper wound care. Eye injury due to the use of the laser is a risk to the subject as well as the operator. The subjects may experience partial or permanent hair reduction. Risks of the topical include temporary irritation, burning or heating up sensation that resolves within 30 minutes

**Benefits:** The subjects may or may not show improvement of melasma on the treatment sites. There is no guarantee of success.

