**Intended Use of the Data:**

The expected end use of the data collected will be for the purpose of best practices in treating melasma on the face. As the purpose of the study is to evaluate the safety and efficacy of low energy diode 1927nm, follow-up photos will be examined for melasma improvement by both the investigator(s) and blinded dermatologist reviewers. A satisfaction questionnaire will be given to patients one month after the final laser treatment. Photos and the satisfaction questionnaire will be examined by the principal investigator and sponsor to determine best practices for use of low energy diode 1927nm in treating melasma in face.

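### Laser sessions 4 to 6 weeks apart do not fit a final visit at week 12 and a follow-up one month after the last laser; the statements agree only when both intervals are about 4 weeks

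*Protocol*

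**What the plan says.** The protocol describes the timing of treatment and follow-up in several places.

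- **Study population:** "Patients will receive three monthly treatments, at 4-6 week intervals". A few sentences later: "Subjects will return for a follow-up visit 3 months after the initial treatment for a total of four visits". The final visit is therefore timed from the first session, while the sessions have a range.
- **Procedure, visit list:** visits 2 and 3, both treatment visits, are at weeks 4 and 8. Visit 4 is at week 12, with grading, photographs and the post-treatment questionnaire. No laser is listed at visit 4, and no visit carries a window.
- **Consent and recruitment text after Study population:** "They will be followed through to completion at the one month follow up".
- **Intended Use of the Data:** "A satisfaction questionnaire will be given to patients one month after the final laser treatment". This anchor is the last session, not the first.
- **Objective A.a:** "To assess for improvement of melasma after completion of three treatments".
- **Clinical Evaluations:** if a treatment is due at a visit, scoring comes before it.

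The Background and the hypotheses also use weeks 4, 8 and 12 for the mMASI.

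**The concern.** The final assessment is timed in two ways: from the first session (week 12, or 3 months) and from the last (one month). The two coincide only if the time between the first and last sessions is fixed, and the 4-6 week range leaves it open. A site that follows the Study population paragraph can comply with it and still miss either the week-12 visit or the one-month follow-up.

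This is more than a clerical matter because the design is split-face. Both sides receive cysteamine and only one receives laser, so time since the last session is a property of one side. Pairing within a patient removes what the two sides share; it does not remove this. The Safety Analysis section anticipates prolonged erythema and, less often, crusting after treatment. The Study population paragraph has redness and hyperpigmentation recorded at visits 2, 3 and 4. Visit 4 also supplies the final grading and the photographs that the blinded reviewers compare with baseline. If patients reach visit 4 at different times after laser, the lasered side is seen at different stages of recovery and response.

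**Working it through.** **Inputs.** Three sessions, with intervals i1 and i2 each from 4 to 6 weeks (Study population). Final visit at week 12 (visit list) or 3 months after the first session (Study population). Last follow-up one month after the last session (Intended Use of the Data; consent and recruitment text).

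**Formulas.** With the first session at week 0:
- third session = i1 + i2
- gap from third session to the week-12 visit = 12 − (i1 + i2)
- the same gap with calendar months: 3 × 365.25 / 12 / 7 = 13.04 weeks, so 13.04 − (i1 + i2)
- follow-up anchored on the last laser, one month taken as 4 weeks = (i1 + i2) + 4

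**The plan's own figure.** The visit list gives i1 = i2 = 4. The third session is at week 8, and 8 + 4 = 12. Week 12 is then both the fixed final visit and one month after the last laser, so the plan's figure reproduces.

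**Across the permitted range:**

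| Intervals (weeks) | Third session (week) | Gap to week 12 (weeks) | Gap to 13.04 weeks | Last laser + 4 weeks |
|---|---|---|---|---|
| 4+4 | 8 | 4 | 5.04 | week 12 |
| 4+5 or 5+4 | 9 | 3 | 4.04 | week 13 |
| 5+5, 4+6 or 6+4 | 10 | 2 | 3.04 | week 14 |
| 5+6 or 6+5 | 11 | 1 | 2.04 | week 15 |
| 6+6 | 12 | 0 (third session due at week 12) | 1.04 | week 16 |

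Any total above 8 weeks breaks either the week-12 visit or a follow-up 4 weeks after the last laser. On the calendar-month reading nothing collides, but the gap still varies by 4 weeks (5.04 − 1.04).

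**How much of the range is affected.** In whole days, each interval can be 28 to 42 days, which gives 15 × 15 = 225 pairs. One pair (28+28) leaves the full 28 days before day 84; the other 224 leave less. One pair (42+42) puts the third session on day 84. These are counts of permitted schedules, not forecasts of how often each would occur.

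**The 6+6 corner.** With a visit at exactly week 12 there are two possibilities. If the third session is given and no later visit is held, there is no separate follow-up. If scoring precedes laser, as Clinical Evaluations requires, the patient is scored after two sessions, contrary to Objective A.a. In that second case the latest laser was at week 6, so the time since laser is 12 − 6 = 6 weeks, not 0.

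**The case against.** The strongest reply is that almost everything else in the protocol points to one schedule. The visit list, the Background and the hypotheses use weeks 4, 8 and 12, and the sentence with the range also calls the treatments monthly. On that schedule week 12 satisfies every statement, and the range is the outlier. This stands as far as it goes: the finding is an internal contradiction, not a prediction of what sites will do. It does not remove the problem, because the range is in operative text and the visit list has no window to limit it.

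A reader might infer something stronger: that some patients will be scored right after laser and others after only two sessions. The documents do not support that. The two-session case needs both intervals at the full 6 weeks and a visit at exactly week 12. Visit 4 lists no laser, and the description of four visits in total implies a follow-up separate from the three treatment visits. The scoring-before-laser rule also makes the zero gap and the two-session case mutually exclusive for one patient. On the calendar-month reading neither arises.

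It is also fair to say that no bias has been shown. The mMASI rates area and darkness and has no item for erythema or crusting, and the protocol gives no figure for how time since laser changes a score. That stands: size and direction are unknown. What remains is that the variation falls on one side only.

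**Conclusion.** The contradiction holds. The statements on session spacing, final visit and follow-up are compatible only when both intervals are about 4 weeks. The calculation takes the 4-6 week range as permitting any spacing within it.

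- With the final visit at week 12, the time from third session to assessment falls from 4 weeks at 4+4 to about 2 weeks at 5+5. At 6+6 the third session coincides with the visit.
- With 3 months as 13.04 weeks, it runs from about 5 weeks to about 1 week.
- With the final visit one month (4 weeks) after the last laser, that visit falls anywhere from week 12 to week 16.

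Scoring after only two sessions is possible at the 6+6 extreme; it is not an established outcome. An effect on the between-side comparison is plausible because laser is given to one side, but the documents do not quantify it. The passages should be reconciled; nothing here says which interval is right.

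**What to change.** Reconcile the Study population paragraph, the visit list for visits 2 to 4, the consent and recruitment text and Intended Use of the Data into one schedule with a stated visit window. Word it so that the final assessment follows all three sessions, as Objective A.a already requires. Record for each patient the actual time from last laser to final assessment. The sponsor decides which interval and which timing anchor (first or last session) to use. Any analysis of patients outside the window is optional and can be left to the statistical analysis plan.

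The cost is a change of protocol wording and the recording of one interval per patient. Depending on the schedule chosen, some patients may attend the last visit on a different date.

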### Procedure:

#### Visit 1 (Screening and Initial Treatment Visit)

- Verify that subject is qualified to participate in the study.
- Ask subject to give personal information, such as name, date of birth, race and ethnicity.
- Review medical and dermatology (skin) history, including history of previous treatments to area being treated.
- Review past and current medications and skin care products.
- See how tall subject is and how much subject weighs
- If subject is a woman and can have children, urine will be tested to see if subject is pregnant. The study doctor or study staff will tell subject if pregnancy test results are positive. The results of the pregnancy testing must be negative in order for subject to be in the study.
- Supply patient with topical cysteamine cream and review instructions for its use
- Identify and examine the area (i.e, side) of face to which the Diode 1927 nm laser will be used (mapping)
- Take photos of face
- Perform grading of melasma
- Perform treatment according to guidelines stated in protocol
- Schedule the next study visit

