**Safety Analysis:**

The potential events that are anticipated post treatment include prolonged erythema, discomfort, and herpes simplex reactivation. Other, less frequent transient potential events associated with any dermatological laser treatment include bleeding, crusting, numbness, itching, blistering and dryness. The occurrence of these events will be considered a treatment response and not an adverse device effect. Anticipated adverse device effects associated with any dermatological laser treatment include scarring, undesirable textural changes and depigmentation.

Grading of these clinical observations will be captured on the case report form under the following scale at each treatment visit and follow up visit:

0=none

1=trace

2=mild

3=moderate

4=severe

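### The protocol contradicts itself on when treatment reactions are recorded, and nowhere places the pain VAS or the 0-4 grading after the laser on the day of treatment

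*Protocol*

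**What the plan says.** All references are to the Protocol.

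- **Objectives, part B.** Two safety objectives concern the treatment session itself: "To evaluate the immediate response to treatment" (B.a) and "To evaluate the subject's assessment of comfort associated with treatments" (B.b).
- **Safety Endpoints.** One endpoint is "Subject assessment of pain and discomfort associated with treatments", scored on an 11-point VAS. No time of administration is given.
- **Study population.** Side effects, with pain and redness named as examples, "will be assessed and recorded at visits 2, 3, 4". Visit 1, the first laser session, is not in that list.
- **Visit 1 list.** "Perform treatment according to guidelines stated in protocol" is followed only by scheduling of the next visit.
- **Visit 2 and 3 list (weeks 4 and 8).** One shared item: "Assess side-effects of the treatment at initial visit".
- **Visit 4 list (week 12).** "Assess side-effects of treatment", with no session specified.
- **Safety Analysis.** Erythema, discomfort, blistering, crusting and similar events are graded 0-4 on the case report form "at each treatment visit and follow up visit".
- **Clinical Evaluations and Photographs.** On a treatment day, clinical scoring comes before the laser, and so do the photographs.

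**The concern.** Pain during a laser session, and the redness or swelling that follows it, are best recorded on the day. The protocol has the objectives and the scales for this but no consistent time point. One set of sections leaves visit 1 out of side-effect recording, and another includes it. Neither says that anything is recorded once the laser has been used.

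The wording of the shared visit 2 and 3 item adds a second fault. Taken literally, the week 8 visit asks again about session 1 and not about session 2.

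At stake are objectives B.a and B.b and the VAS endpoint. Safety Analysis counts events such as erythema, discomfort and blistering as treatment response and not as adverse device effects, so device-effect reporting would not be expected to pick them up. The graded form and the VAS are where they would appear. A same-day observation that was never made cannot be recovered at the analysis stage, so this belongs in the protocol's visit schedule and cannot be left to an analysis plan.

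**Working it through.** The protocol gives no figure for this point to reproduce. The check sets the sections side by side and works out the time from each session to the first assessment that covers it.

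**Step 1: is visit 1 covered?**

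| Section | Visit 1 | Visits 2 and 3 | Visit 4 | Timed after the laser? |
|---|---|---|---|---|
| Study population | no | yes | yes | not stated |
| Visit lists | no | yes, about the initial session | yes | not stated |
| Safety Analysis (0-4 grades) | yes | yes | yes | not stated |
| Safety Endpoints (VAS) | not stated | not stated | not stated | not stated |
| Clinical Evaluations (clinical scoring) | before the laser | before the laser | no laser | no |
| Photographs | before the laser | before the laser | no laser | no |

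The first two rows conflict with the third on visit 1. No row places a record after the laser on the same day.

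**Step 2: look-back times if the Study population text and visit lists are followed and their assessments only look back.** Inputs: visits at weeks 0, 4, 8 and 12 (visit lists), and a 4-6 week interval between sessions (Study population).

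- Session 1 to visit 2: 4 - 0 = 4 weeks nominally, 4-6 weeks under the stated interval.
- Session 1 to visit 3, the look-back that the shared item literally asks for: 8 - 0 = 8 weeks nominally, 2 × 4 to 2 × 6 = 8-12 weeks under the stated interval.
- Session 2 to visit 3, if the item was meant to refer to the preceding session: 8 - 4 = 4 weeks nominally, 4-6 weeks under the stated interval.
- Session 2 to visit 4, the first assessment that can cover it if the item is read literally: 12 - 4 = 8 weeks nominally, or 12 - 6 = 6 to 8 weeks if session 2 falls at weeks 4-6.
- Session 3 to visit 4: 12 - 8 = 4 weeks nominally.

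**Step 3: sessions with a same-day post-laser record.** With 20 subjects and three sessions each there are 20 × 3 = 60 sessions. The count depends on the reading:

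- Study population text and visit lists followed, assessments look back only: 0 of 60.
- The same sections followed, but sites also record the current session after the laser at visits 2 and 3: 20 × 2 = 40 of 60. The missing 20 are the visit 1 sessions (20/60 = one third).
- Safety Analysis followed, grading done before the laser in line with clinical scoring: 0 of 60. The visit 1 grade is then a pre-treatment baseline.
- Safety Analysis followed, grading done after the laser: 60 of 60.

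The protocol does not say which of these applies, and sites or staff could reasonably act on different ones.

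**The case against.** The strongest reply is that the protocol, read as a whole, does provide for recording at visit 1. Safety Analysis asks for grading at every treatment visit, and visit 1 is one. The VAS concerns pain associated with treatments, and the session is estimated at 90 minutes including post-treatment procedures, so same-day use fits naturally. Unanticipated events during or after laser use must be reported whenever they occur, and subjects can reach the investigators between visits. Dryness and hyperpigmentation can be examined at a later visit without recall. The reference to the initial visit looks like a slip from merging visits 2 and 3 under one heading, and the visit 4 item is not tied to any session. The case report form, which may settle the timing, is not shown.

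Much of this stands. A reader might infer that nothing is recorded after the laser at visit 1, that side effects are recorded only at visits 2, 3 and 4, and that the objectives therefore rest on memory weeks later. The documents do not support that as a settled fact: Safety Analysis says otherwise about visit 1, and the time of the VAS is open. For the same reason, one third of sessions without a same-day record, or a recall of at least four weeks, holds only under particular readings. Nor do the documents establish that the error would run towards understating harm.

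The reply does not remove the contradiction. Being compatible with same-day recording is not the same as requiring it, and the only ordering rules in the protocol put scoring and photographs before the laser. A drafting slip in a visit list is still the instruction that staff will follow.

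**Conclusion.** The point holds as a contradiction and a gap in timing. The Study population text and the visit lists disagree with Safety Analysis about visit 1. No section puts the 0-4 grades or the VAS after the laser on the treatment day. The visit 3 item, as worded, passes over session 2.

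The size is conditional. If the Study population text and visit lists are followed, and their assessments only look back, no session has a same-day post-laser record. Session 1 is first asked about 4-6 weeks later and session 2 not until visit 4, 8 weeks later on the nominal schedule. Objectives B.a and B.b and the VAS endpoint could not then be answered reliably. If Safety Analysis governs and grading follows the laser, the gap for the graded reactions disappears, and the VAS still needs a stated time.

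The primary efficacy comparison is not affected. The matter should be corrected because the data at risk cannot be restored later and the correction is cheap.

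**What to change.** Reconcile the three visit lists, the Study population text, Safety Endpoints and Safety Analysis so that they give one schedule:

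1. At visits 1, 2 and 3, record the pain VAS and the existing 0-4 grades after the laser, before the subject leaves. Add both to the visit lists.
2. At visits 2, 3 and 4, ask about side effects of the session at the preceding visit. Replace the reference to the initial visit in the shared list.
3. State that the rule placing clinical scoring before the laser does not apply to these post-laser records.

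The cost is revised wording and a few extra minutes per session. Subjects are already on site and both scales are already in the protocol. Treatment is unchanged. Grading each side of the face separately is an option but is not needed to resolve the contradiction.
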